: 24 hours inside the metabolic chamber (*ad libitum* diet)

Quest.: self-administered questionnaires and computerized tasks

OGTT: oral glucose tolerance test

DXA: dual energy X-ray absorptiometry for body composition assessment

VO₂ max: graded-cycle ergometry

Chamber: 24-h measure of EE in the metabolic chamber

Vending: computerized vending machines for *ad libitum* food intake measurement

332 Volunteers will provide informed consent prior to entering the study. Subsequently, they will
333 be screened and interviewed for eligibility. During screening, a medical history will be obtained as
334 well as a physical exam and resting 12 lead electrocardiogram. Blood will be drawn for screening tests
335 including complete blood cell count, platelet count, glucose, electrolytes, urea nitrogen, creatinine,
336 liver function tests (total protein, albumin, bilirubin, AST, ALT, gamma-GT, alkaline phosphatase),
337 thyroxine stimulating hormone (TSH), calcium and phosphorus. Urine will be collected for complete
338 urinalysis, urinary hCG (pregnancy test for females only) and drug testing. All subjects who meet
339 inclusion and exclusion criteria and agree to participate will be admitted to the clinical research unit
340 for about 23 days to complete the study. Initial demographic information will be collected on all
341 subjects including comorbidities, race, gender, weight, height and waist, thigh and neck
342 circumferences. There is nursing staff available 24 hours a day.

343 **Randomization**

344 Randomization will be done using a permuted block randomization design with a block size of
345 6 stratified by sex to account for potential order effects of cold interventions (described below).
346 Specifically, half the subjects will undergo first the assessment of *ad libitum* food intake on the
347 vending machines the day following the cold intervention inside the metabolic chamber (as shown in
348 Figure 1,), with the other half undergoing first the *ad libitum* food intake assessment the day of the
349 cold exposure inside the metabolic chamber (Figure 1). The random allocation sequence will be
350 created by a statistician who does not have subject contact.

351 **Admission**

352 A description of the inpatient phase of the study is provided below. The specific day numbers on which
353 procedures occur represent a common scenario. The precise day may vary due to normal subject scheduling

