645 estradiol and progesterone (women only). Urine pregnancy test (β -hcg) will be done in females only.
646 The DXA scan will not be performed if the pregnancy test is positive.

647 **Blood Withdrawal**

648 Blood withdrawal will remain within the NIH guideline of <10.5 mL/kg or <550 mL (whichever
649 is smaller) every 8 weeks for research purposes. The total amount of blood drawn is detailed below.

650

651

Tests	Amount
Screening lab work	32 mL
OGTT	151 mL
Fasting blood measurements	
EBL chamber (pre- and post-)	76 mL
CIT chamber (pre- and post-)	60 mL
FST chamber (pre- and post-)	60 mL
Total (baseline admission):	379 mL
Outpatient visits	
6 months	32 mL
1 year	32 mL
Total:	443 mL

652

653 **Sample Size Calculation**

654 The sample size calculation to answer the primary research question is based on the number
655 of patients needed to demonstrate an association between any change in EE due to interventions and
656 subsequent change in energy intake. In preliminary analyses using data from our clinical research unit
657 [13], the cross-sectional Pearson correlation between unadjusted 24-h EE during energy balance and
658 energy intake is 0.46 ($p<0.0001$). A target sample size of 46 participants will provide a power of
659 greater than 0.80 with an alpha of 0.05 to detect a 0.40 correlation ($r^2=0.16$) using simple linear
660 regression assuming that the association between change in EE and change in energy intake will be
661 the same as that between EE and energy intake. However, any finding will subsequently be adjusted
662 in multivariate linear regression analysis for age, sex, race, fat mass and fat free mass (5 covariates),
663 which requires a minimum of 50 volunteers. In addition, given the number of analyses that will be
664 done, an alpha of 0.01 is likely more appropriate. Therefore, to detect a correlation of 0.4 with a
665 power >0.80 at an alpha = 0.01, a total of 68 subjects will be enrolled for the core study (Table 2).

666

667 **Table 2. Sample size calculations achieving a statistical power ≥ 0.8 .**

	$\alpha=0.05$	$\alpha=0.01$	$\alpha=0.005$	$\alpha=0.001$
r=0.50	n=29	n=41	n=47	n=59
r=0.40	n=46	n=68*	n=77	n=98
r=0.30	n=84	n=124	n=142	n=181

668 r: Pearson's unadjusted correlation between change in EE and change in energy intake

669 α : significance level (2-sided)

670 *: Sample size for the final analysis

671

672 An interim analysis will be conducted when a target sample size of 47 subjects complete the

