722 mass. In evaluating the relationship between altered EE by cool exposure/fasting and *ad libitum* food
723 intake, the concomitant RQ will also be included as further covariate in the multivariate model. Lastly,
724 sensitivity analyses accounting for the SPA inside the metabolic chamber will be done. Although we
725 anticipate that the wash-out period will remove any carry-over effect, potential order effects arising
726 from the cross-over design of the study will be assessed by including a dichotomous variable for the
727 sequence effect of interventions (e.g., 0 = “cold exposure & subsequent *ad libitum* food intake”; 1 =
728 cold & concomitant *ad libitum* food intake) in the multivariate models assessing the association
729 between change in EE and change in energy intake. Student t-tests will be also calculated to
730 determine if the change in EE or the change in energy intake differ between these two groups. If no
731 difference exists in the outcome variables between these 2 groups and the dichotomous variable is
732 not significant in the multivariate model, we will determine that no evidence for an order effect exists
733 and leave the dichotomous variable out of the final multivariate model. If there will be evidence of an
734 order effect, we will include the dichotomous variable in the multivariate model to ‘adjust’ for the
735 order effect.

736 To follow-up the regression analyses and assess potential causality linking EE to energy intake,
737 mediation analysis based on hierarchical multiple regression models as outlined in [66] will be used to
738 evaluate whether the effect of increased EE on energy intake is exerted through the influence of
739 mediators, including hormonal changes, RQ appetite sensations, behavioral and neurocognitive
740 scores. The Sobel test [67] will be used to test the significance of the mediation effect.

741 For all hormonal measures, the change in concentrations induced by the interventions will be
742 compared to the baseline fasting concentrations drawn prior to the energy balanced 24-h EE
743 assessment using paired t-tests for normally distributed data or the Wilcoxon nonparametric test for
744 skewed data. A sample size of 68 subjects will provide greater than 80% power with an alpha of 0.05
745 to detect a minimum mean expected decrease in fasting leptin, as a representative hormone, of
746 -1.8 ± 6.0 ng/mL as observed in prior studies measuring leptin concentrations during 24-h fasting [1].

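### The adjusted model drops the randomised sequence term after a non-significant composite pre-test that has no stated alpha and no sizing; the term should always stay, although the effect on the result is small

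*Combined protocol and SAP*

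**What the plan says.** Under Randomization, participants are allocated in permuted blocks, stratified by sex, to one of two orders of the cold sessions, half to each. The stated reason is possible order effects.

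Under Data Analysis, a 0/1 sequence variable enters the multivariate models relating EE change to intake change. Student t-tests also compare the two sequence groups on each change variable. If the groups do not differ and the variable is "not significant in the multivariate model, we will determine that no evidence for an order effect exists", the plan will then "and leave the dichotomous variable out of the final multivariate model". In the other branch, given evidence of an "order effect, we will include the dichotomous variable in the multivariate model".

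No significance level is attached to these checks. The end of Data Analysis sets two-sided 0.01 for primary outcome tests and 0.05 for secondary ones, without saying which governs the pre-test. The sample size tables concern a different quantity, described in the note to Table 2 as "r: Pearson's unadjusted correlation between change in EE and change in energy intake". Nothing elsewhere in the document keeps the sequence term unconditionally.

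**The concern.** Sequence is part of the design, so the analysis would ordinarily carry it whatever the data show. Here it stays only if the same outcome data give a significant result, and a non-significant result is read as no order effect. A trial of 68, split in half and sized for a correlation, may well miss a moderate order effect.

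Three things are at stake. The adjusted model is chosen after the outcomes are seen. Because the level is unstated, two analysts following the text could arrive at different final models. And where an order effect is missed, its variance, and any shift common to both change variables, stays in the adjusted regression.

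**Working it through.** **The plan's own figure.** For r = 0.40, two-sided alpha 0.01 and power 0.80, the plain Fisher formula is n = ((z_a + z_b)/atanh r)² + 3 = ((2.576 + 0.842)/0.4236)² + 3 ≈ 68.1, which rounds up to 69. With a t-based critical value and the small-sample bias term it gives 68, with power 0.803. The plan states 68 and 0.804, so its sizing is reproduced. It gives no corresponding figure for detecting an order effect.

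**One between-sequence t-test.** Inputs: 34 per sequence (half of 68). Assumed, because the document gives neither: order effects d of 0.2 to 0.8 SD, and a pre-test level of 0.05 or 0.01. The noncentrality is d/√(1/34 + 1/34) = 4.12d on 66 degrees of freedom.

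| Order effect | Power at 0.05 | Power at 0.01 |
|---|---|---|
| 0.3 SD | 0.23 | 0.09 |
| 0.5 SD | 0.53 | 0.29 |
| 0.7 SD | 0.81 | 0.59 |
| 0.8 SD | 0.90 | 0.74 |

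The effect detectable with 80% power is 0.69 SD at 0.05 and 0.85 SD at 0.01. If the trial grows to 124 (62 per sequence), power at 0.5 SD is 0.79 or 0.57, and at 0.3 SD it is 0.38 or 0.18.

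**The full rule.** The term is dropped only if both t-tests and the coefficient are non-significant. This was simulated at N = 68, with six independent normal covariates, no dropout, no true EE–intake association, and 20,000 runs per setting. Type I error is for the final slope test at 0.01; bias is in the standardised slope. Each pair gives the result for a pre-test at 0.05 and then at 0.01.

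| Order effect | Term dropped | Type I error under the rule | Slope bias under the rule |
|---|---|---|---|
| None | 89% / 98% | 0.009 / 0.011 | 0 / 0 |
| 0.5 SD, intake only | 42% / 68% | 0.009 / 0.011 | about 0 / 0 |
| 0.3 SD on both | 57% / 82% | 0.010 / 0.011 | 0.005 / 0.014 |
| 0.5 SD on both | 21% / 49% | 0.010 / 0.012 | 0.007 / 0.016 |

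Hand check at 0.05, ignoring the coefficient test, which can only lower the drop rate: 0.5 SD on both gives (1 − 0.53)² ≈ 22%; 0.3 SD on both gives (1 − 0.23)² ≈ 59%; 0.5 SD on intake only gives (1 − 0.53) × 0.95 ≈ 45%. These agree with the table. A repeat simulation matched the drop rates to within about one percentage point. Allowing for simulation error, type I error does not exceed about 0.013 and bias does not exceed about 0.02.

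**Always keeping the term.** Type I error is 0.009 to 0.010 in every setting. With a true r of 0.40 and no order effect, power of the adjusted test is about 0.75 with the term kept and 0.76 under the rule. With a pre-test at 0.01 and 0.5 SD shifts on both variables, power is about 0.78 under the rule against 0.75 kept when the shifts have the same sign (partly through upward bias in the slope). It is about 0.71 against 0.75 when they have opposite signs.

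**The unadjusted correlation.** A shift of d in both variables, with no true association, induces r = 0.25d²/(1 + 0.25d²): 0.022 at 0.3 SD and 0.059 at 0.5 SD. This is the same under either branch of the rule, because the rule acts only on the multivariate model.

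**The case against.** The strongest reply is that the plan already deals with order: allocation is randomised, washout days separate the sessions, a check is written down in advance, and adjustment follows if the check is positive. The pre-test is also a composite, so the term survives more often than a single-test power suggests. With 0.5 SD on both variables and a level of 0.05, it is kept in about 79% of runs. A one-variable shift, where the rule fails more often, creates no spurious association. And the calculations show no setting in which the error rate or slope moves much.

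Most of this stands, and it limits the point to one of pre-specification. It does not rescue the rule. The plan only anticipates that washout will suffice, and period or habituation effects need not wash out. The drop rates above already include all three tests. They also roughly double in the setting just quoted if the unstated level is 0.01.

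A reader might infer that the rule contaminates the primary correlation. The documents do not support that: sizing and the interim analysis rest on the simple correlation, adjustment comes afterwards, and the rule touches only the adjusted model. A reader might also infer that keeping sequence would fix that model fully in advance. It would not, because other choices stay open, such as absolute or percent change and the covariate list, which differs between Sample Size Calculation and Data Analysis.

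**Conclusion.** The point holds as a minor weakness of pre-specification. A randomised design factor is kept or dropped on a composite pre-test with no stated level and no sizing. At N = 68 that pre-test drops the term in roughly one fifth to four fifths of trials that have a 0.3 to 0.5 SD order effect. A non-significant result cannot carry the conclusion that the plan draws from it.

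The description of the pre-test as weak is limited to small and moderate effects. It does not hold for order effects of about 0.7 SD or more at a level of 0.05, and at N = 124 a single test reaches 0.79 power for 0.5 SD. The primary result is not put in doubt: adjusted type I error stays at about 0.009 to 0.013 against 0.01, slope bias is at most about 0.02, and power shifts by up to about 4 points in either direction.

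These figures rest on assumptions that the documents do not supply: the pre-test level, the order-effect sizes, independent normal covariates, and complete data in equal groups.

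**What to change.** In Data Analysis, delete the rule that makes the sequence variable conditional on significance. State instead that it is included in all adjusted models of EE change against intake change. Report its estimate with a confidence interval in place of a yes/no finding on order effects; the between-sequence t-tests can remain as description. Sex, the stratification factor, is already a covariate in these models, so nothing needs adding for it.

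The cost is a one-sentence edit and one degree of freedom, about 0.01 of power at N = 68 and r = 0.40 when there is no order effect.

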673 baseline admission. This sample size will provide 80% power ($\alpha=0.005$) to detect a simple

674 correlation of 0.5 between change in EE due to any intervention and change in energy intake. The

675 alpha level for this interim analysis is set to 0.005 based on the alpha spending function approach

676 [[64, 65]]. The alpha level for the final analysis will remain at 0.01. More importantly, the interim

677 analysis will allow us to assess whether there is likely to be a significant correlation once the full

678 sample size is reached or whether the null hypothesis is highly likely to be accepted. If the correlation

679 within the first 47 subjects is <0.2 , the study will be stopped as the null hypothesis will be highly likely

680 to be accepted. However, if the correlation is much stronger than anticipated, the study will continue

681 to obtain adequate sample size for adjusting for covariates and answering the secondary research

682 questions. If the interim correlation is between 0.2 and 0.4, the final sample size will be increased

683 from 68 to 124 subjects to provide 80% power at an alpha of 0.01 to detect a more moderate

684 association. Achieved power as a function of final sample size, alpha and correlation value between

685 change in EE and energy intake is reported in Table 3. Assuming a 30% dropout rate, we will ask for a

686 total enrollment of 160 subjects.

687

688 **Table 3. Power calculations based on different values of alpha (α), correlation value (r) and**
 689 **sample size (n).**

α	r	n	Power
0.001	0.30	47	0.103
		68	0.208
		124	0.544
	0.40	47	0.308
		68	0.547
		124	0.915
	0.50	47	0.635
		68	0.873
		124	0.997
0.005	0.30	47	0.223
		68	0.378
		124	0.727
	0.40	47	0.503
		68	0.732
		124	0.969
	0.50	47	0.803*
		68	0.949
		124	0.999
0.01	0.30	47	0.301
		68	0.470
		124	0.799
	0.40	47	0.598
		68	0.804**
		124	0.982
	0.50	47	0.863
		68	0.969
		124	1.000

690 *: interim analysis

691 **: final analysis

692
 693 **Data Analysis**

694 Our primary outcome will be the association between the change in EE and the change in
 695 energy intake induced by the interventions (cool temperature exposure and fasting). As the purpose
 696 of this protocol is to evaluate the effects of altered EE on food intake regardless of the type of
 697 intervention, only within-subject analyses rather than between-interventions analyses will be carried

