747 This sample size provides a similar power to detect a correlation of -0.30 at an alpha of 0.05 between
748 the decrease in any of the hormones and cold induced thermogenesis or the expected increase in
749 energy intake. Hormonal changes will be evaluated as possible contributors to the altered 24-h EE
750 and subsequent energy intake first in correlation analyses stratified by type of intervention (i.e., cold
751 exposure and 24-h fasting) and then using similar mixed models as described above. Additionally,
752 behavioral and cognitive test scores will be evaluated as possible predictors of the EE-energy intake
753 link, again using correlations and mixed models. The minimum expected correlation detectable in 68
754 subjects for any of the scores with changes in energy intake will equal 0.30, as reported above.
755 Differences in core body temperature and skin temperatures from measures during energy balance
756 will be calculated for fasting and cold exposure. The significance of these changes will be assessed
757 using one-sample t-tests. The association between these changes and percent body fat as well as EE
758 responses will be assessed using correlation coefficients as above, and again, the minimum detectable
759 correlation with 68 subjects equals 0.30. Significant associations will be evaluated further with mixed
760 models to account for repeated measures, sex, race and age and other potential confounders.
761 Associations between EE responses to each intervention and absolute weight change at each
762 follow-up visit will be quantified by regression models accounting for age, sex, race, and baseline

763 weight. All longitudinal analyses for future weight change will be confirmed using percent change in
764 weight as the dependent variable instead of absolute weight change. Similar models will be calculated
765 for the absolute changes in fat mass and fat free mass including baseline measures as covariates. In
766 case of significant associations between the EE responses to different intervention and weight
767 change, full regression models will be calculated to determine independence of the identified
768 predictors. Mixed model analysis will be used to evaluate the predictive effect of baseline EE
769 measures in relation to the body weight trajectory including all the follow-up visits and accounting for
770 repeated measures. The Compound Symmetry (CR) and the AR(1) covariance structures will be

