771 evaluated and compared by the BIC statistic to identify the best model for weight data over time.
772 Changes in EE after 24-h of fasting and its association with changes in body weight at 6 months and 1
773 year will be combined with data from prior studies (using the exact same methodology) to increase
774 the statistical power of the weight change analysis (currently we have >60 subjects with complete
775 data available at baseline).

776 Statistical analysis will be performed using SAS with E-guide (SAS Institute, Cary, NC). All tests
777 of primary outcome measures will have a 2-sided Type 1 error of $p=0.01$. For the secondary outcome
778 analyses, we will control for Type 1 error at the level of the comparison with $p=0.05$ as each
779 hypothesis is substantively important and stated *a priori*.

780 **Informed Consent Process**

781 Written informed consent will be obtained from the participant prior to any screening visits,
782 study procedures or treatments. The person obtaining consent will explain the study in language
783 understandable to the subject. Sufficient time and opportunity will be given for discussion of the
784 research as well as to answer any questions they may have, taking care to minimize or eliminate the
785 perception of coercion or undue influence. The participant and the investigator will sign the current
786 IRB-approved informed consent document. A copy of the consent will be given to the subject for
787 future reference. The signed documents will be sent to the Medical Records Department for
788 placement in the subject's permanent record.

789 Participants will have the opportunity to carefully review the written consent form, either as a
790 physical or electronic document, and ask questions prior to signing. Participants will be informed that
791 participation is voluntary and that they may withdraw from the study at any time, without prejudice.

792 The consenting process may be performed using the NIH iMedConsent platform (which is 21
793 CFR Part 11 compliant). If the iMedConsent platform is used, then the participant and consenting
794 investigator will review and sign the current IRB-approved electronic informed consent document
795 using a hand signature (e.g., signing using a finger, stylus, or mouse). Electronic signatures (i.e., the
796 “signature” and a timestamp are digitally generated) will not be used. If a paper copy of the IRB-

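### Mediation is tested only with the Sobel test, which is conservative at n=68 and, for modest paths, loses power that a Monte Carlo interval would keep

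*Combined protocol and SAP*

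**What the plan says.** The Data Analysis section says that "mediation analysis based on hierarchical multiple regression models as outlined in [66] will be used to" judge whether the effect of raised energy expenditure (EE) on intake runs through "mediators, including hormonal changes, RQ appetite sensations, behavioral and neurocognitive" scores. For significance it adds: "The Sobel test [67] will be used to test the significance of the mediation effect". No bootstrap, Monte Carlo or other interval for the indirect effect is named anywhere, and no path size, indirect effect or power is given for this analysis.

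The nearest planning values lie elsewhere in the document. For hormones at n=68, Data Analysis states "This sample size provides a similar power to detect a correlation of -0.30 at an alpha of 0.05 between" the hormone change and either cold-induced thermogenesis or the rise in intake. The Sample Size Calculation section plans on a correlation of 0.40 between EE change and intake change. The core sample is 68, but if the interim correlation lies between 0.2 and 0.4 the final sample is raised "from 68 to 124 subjects to provide 80% power at an alpha of 0.01 to detect a more moderate" association. Secondary analyses are tested at 0.05 per comparison and primary outcomes at two-sided 0.01. The text does not say which level applies to mediation; I take it as secondary.

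**The concern.** The product of two estimated coefficients is not normally distributed when the paths are modest and the sample is small. A test that treats it as normal then rejects less often than its nominal level, whether or not mediation is present.

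Mediation is how the plan moves from an association between EE and intake to a mechanism. Table 4 labels 14 hormones, the ketone panel, the urinary measures and the appetite scales, among others, as potential mediators. With an over-conservative test, some true mediators would be reported as unsupported for a reason that lies in the test and not in the data.

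**Working it through.** **Inputs from the documents.** n=68, or 124 after the interim; alpha 0.05 (secondary), with 0.01 (primary) as a sensitivity check; planning correlations 0.30 and 0.40; five adjustment covariates.

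**Assumptions, not in the documents.** One mediator, standardised normal variables, direct effect 0.2 unless stated, two-sided tests.

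**Step 1: the plan's own figure.** Table 3 gives power 0.804 for r=0.40, n=68, alpha 0.01. By Fisher's z, √65 × atanh(0.40) − 2.576 = 8.062 × 0.4236 − 2.576 = 0.84, so power is 0.800. With the bias correction and a t critical value it is 0.803. The figure reproduces. There is no mediation figure to reproduce.

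**Step 2: why Sobel is conservative.** With a the path from EE change to mediator and b the path from mediator to intake change,

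z = ab / √(a²·SE_b² + b²·SE_a²), so 1/z² = 1/z_a² + 1/z_b².

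At a=b=0.30 and n=68, SE_a ≈ √(0.91/66) = 0.117. The residual variance of the outcome is 1 − (0.09 + 0.04 + 0.036) = 0.834, so SE_b ≈ √(0.834/(65 × 0.91)) = 0.119. Then z_a ≈ 2.56 and z_b ≈ 2.53. Each path exceeds 1.96, yet the Sobel z is about 1.80. Two equal paths must each reach 1.96 × √2 = 2.77 before Sobel declares mediation.

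**Step 3: simulated Type I error, n=68, nominal 0.05.**

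| a, b | Sobel | Monte Carlo | Percentile bootstrap |
|---|---|---|---|
| 0, 0 | 0.000 | 0.003 | 0.004 |
| 0.4, 0 | 0.022 | 0.052 | 0.060 |
| 0, 0.4 | 0.016 | 0.040 | 0.045 |

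A separate simulation put Sobel between 0.000 and 0.041. Another, with b=0 and a=0.4, 0.5 and 0.6 (4,000 data sets), gave Monte Carlo 0.046, 0.053 and 0.058, and bootstrap 0.055, 0.061 and 0.065.

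**Step 4: simulated power, alpha 0.05** (2,000 to 3,500 data sets; standard error about 0.01 near power 0.5).

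| n | a, b | Sobel | Monte Carlo | Bootstrap | Loss against Monte Carlo (points) |
|---|---|---|---|---|---|
| 68 | 0.2, 0.2 | 0.04 | 0.13 | 0.14 | 9 |
| 68 | 0.3, 0.3 | 0.28 | 0.49 | 0.49 | 21 |
| 68 | 0.35, 0.35 | 0.53 | 0.72 | 0.72 | 18 |
| 68 | 0.4, 0.3 | 0.46 | 0.63 | 0.62 | 16 |
| 68 | 0.4, 0.4 | 0.75 | 0.85 | 0.85 | 10 |
| 68 | 0.5, 0.3 | 0.54 | 0.63 | 0.63 | 9 |
| 68 | 0.5, 0.5 (direct 0.1) | 0.96 | 0.98 | 0.98 | 2 |
| 68 | 0.6, 0.6 (direct 0) | 1.00 | 1.00 | 0.99 | 0 |
| 124 | 0.3, 0.3 | 0.74 | 0.85 | 0.85 | 12 |
| 124 | 0.4, 0.4 | 0.99 | 0.99 | 0.99 | under 1 |

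A repeat simulation at n=68 gave 0.28 vs 0.47, 0.50 vs 0.69 and 0.75 vs 0.86 at paths 0.30, 0.35 and 0.40.

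**Step 5: sensitivity at n=68.**
- Five covariates: Sobel 0.25 vs Monte Carlo 0.44 at paths of 0.3, and 0.68 vs 0.82 at 0.4.
- Planning values read as marginal correlations, with EE–intake r=0.40. For 0.30, b = (0.30 − 0.30 × 0.40)/(1 − 0.09) = 0.198 and power is 0.12 vs 0.26, a loss of 14 points. For 0.40, b = (0.40 − 0.16)/0.84 = 0.286 and power is 0.46 vs 0.63, a loss of 17.
- Alpha 0.01: the loss is 17 points at paths of 0.3 (0.05 vs 0.22) and 30 at 0.4 (0.34 vs 0.64).

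**Step 6: the interim rule.** The total effect is 0.2 + ab, that is 0.29, 0.32 and 0.36 at paths of 0.30, 0.35 and 0.40. All lie in the band that leads to 124. Applying the rule to the correlation in the first 47 subjects (6,000 runs), the trial ends at 68 in 21%, 29% and 39% of runs and goes to 124 in 54%, 54% and 50%; the rest stop. Among trials that continue, Sobel vs Monte Carlo power is 0.64 vs 0.78, 0.80 vs 0.88 and 0.90 vs 0.94. The average losses are about 14, 9 and 4 to 5 points.

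**The case against.** The strongest reply is that the size of the loss is assumed rather than derived from the plan. A reader might infer that a loss of 10 to 20 points follows from n=68 itself. It does not: the documents state no path sizes, the gap is widest for paths of about 0.3 to 0.4, and the plan's own interim rule would often move the trial to 124, where the gap is smaller. This objection stands, and the range has to be reported with its conditions.

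A reader might also infer that a resampling interval holds Type I error at or below 0.05. That is too strong. When b=0 and a is large, both alternatives run slightly above nominal, the bootstrap more so. With many mediators each tested at an unadjusted 0.05, this deserves mention. It favours the Monte Carlo interval over the bootstrap, but does not rescue a test with error of 0.00 to 0.04.

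Nor do the documents support a complaint about a faulty Sobel confidence interval. The plan uses Sobel for significance only and proposes no interval.

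Finally, the replacement is no cure for a small sample. At paths of 0.3 and n=68 it still misses a true mediator about 51% of the time, against 72% for Sobel. Mechanism is also examined by correlations and mixed models. These points limit the consequence; they do not give a reason to prefer Sobel.

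**Conclusion.** The point holds in a conditional form. Sobel is the only mediation test named, and at n=68 its Type I error is about 0.00 to 0.04 against a nominal 0.05. With one mediator, normal errors, a direct effect of 0.2, two-sided alpha 0.05 and standardised paths of 0.3 to 0.4, it gives up about 10 to 21 points of power to a Monte Carlo interval. Outside that region, or at n=124, the loss is smaller and can vanish. The path range is an assumption, chosen because the plan's own planning correlations are 0.30 and 0.40.

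A reader might infer that the primary conclusion is at risk or that mediators would be falsely claimed. Neither follows. The test of EE change against intake change does not use Sobel, and the error runs toward missed mediators. This is a worthwhile improvement to a secondary, explanatory analysis.

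**What to change.** Replace the Sobel test with a pre-specified Monte Carlo 95% interval for the indirect effect: draw a and b from normal distributions with their estimated coefficients and standard errors, form the products, and take the 2.5th and 97.5th percentiles. Call mediation significant when the interval excludes zero. Add a percentile bootstrap interval as a sensitivity analysis. Fix the number of draws and the seed, state that mediation is tested at the secondary level of 0.05, and settle all this before the mediation models are run, so that the choice of test cannot depend on the results.

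The cost is a few lines of code around the same regressions, with no new data or visits. The trade-off is Type I error close to 0.05 (in simulation up to about 0.058 for Monte Carlo and 0.065 for the bootstrap when b=0 and a is large) instead of well below it.
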